The underlying causes of death will be classified as coronary [ICD-9:410-414], other heart failure [ICD-9:402, 404, 428], cerebrovascular, other vascular, cancer related, or other and unknown causes by the endpoint committee who will be blinded to treatment allocation. From an analysis viewpoint statistical censoring is only enforced at the time of death.

Investigators may be requested by the endpoint committee to provide all relevant documentation to substantiate the diagnosis of a study endpoint.

6. Safety Reporting

A summary of the organisation of reporting adverse events and endpoints is shown in the following figure:

* Rejected endpoints might potentially be SAE's.

a. Endpoints

Study endpoints are classified as:

Primary endpoints

(i) Non-fatal MI (symptomatic and silent MI) + fatal CHD

Secondary endpoints

(i) Non-fatal MI (symptomatic only) + fatal CHD

(ii) All cause mortality

(iii) Cardiovascular mortality

(iv) Fatal and non-fatal stroke

(v) Fatal and non-fatal heart failure

(vi) Total coronary endpoints = fatal CHD + non-fatal MI (symptomatic and silent) + chronic stable angina + unstable angina + fatal and non-fatal heart failure

(vii) Total cardiovascular events and procedures = cardiovascular mortality + non-fatal MI (symptomatic and silent) + unstable angina + chronic stable angina + life threatening arrhythmias + non-fatal heart failure + non-fatal stroke + peripheral arterial disease + revascularisation procedures, and retinal vascular thromboses.

Tertiary endpoints

(i) Silent MI

(ii) Unstable angina

(iii) Chronic stable angina

(iv) Peripheral arterial disease

(v) Life threatening arrhythmias (VF or sustained VT or complete heart block)

(vi) Development of diabetes mellitus

(vii) Development of renal impairment

(viii) With and without metabolic syndrome*

* As defined according to NCEP III except for replacing waist-hip ratio with BMI > 30 as patients with triglycerides ≥ 1.69 mmol/l, HDL-C for males < 1.03 mmol/l, for women < 1.29 mmol/l, BP $\geq 130/85$ mmHg, fasting glucose ≥ 6.1 mmol/l.

These events are not considered as serious adverse events.

During the study period, an event classified as an endpoint must be reported by mail to the Scandinavian Co-ordinating Centre as soon as the investigator is informed. If an investigator receives information of an endpoint that has occurred within 30 days after the study period this also has to be reported to:

[figure not shown]
Endpoint Administrator

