Scandinavian Co-ordinating Centre/Ascot
Clinical Research Institute
[name]
[name]
Sweden

In the case of a patient death, a summary of available autopsy findings must be submitted as soon as possible to the Scandinavian Co-ordinating Centre. The investigator should ensure that information on such cases reported by telephone or other means and information entered in the case record forms are accurate and consistent. The endpoints are sent on a continuous basis to the Endpoint Committee for evaluation of whether they qualify for inclusion as an endpoint or not.

The Endpoint Committee, who are blinded as to study therapies, will evaluate and classify the endpoints. Confirmed endpoints will be reported back to the Scandinavian co-ordinating centre who will forward these data to the Data Safety Monitoring Committee (DSMC). Those events considered to be serious adverse events and not endpoints by the Endpoint Committee will be reported immediately to the Scandinavian Co-ordinating Centre for immediate reporting as a serious adverse event to Pfizer Clinical Research Group in the relevant country.

Endpoints will be handled as follows:

Endpoint Data Flow

b. Serious Adverse Events

Serious Adverse Events includes any experience which is not a study endpoint that suggests a significant hazard, such as events which:

- (1) are life threatening
- (2) results in a persistent or significant disability/incapacity
- (3) require inpatient hospitalisation or prolongation of a hospital stay due to other causes than endpoints (see above)
- (4) result in congenital anomaly/birth defect
- (5) require medical intervention to prevent any one of the above.(For further details please refer to the Ascot Adverse and Serious Adverse Event manual)

[figure not shown]
It should be emphasised that, regardless of the above criteria, any additional adverse experience, which the investigator considers serious, should be reported immediately.

An event classified as a Serious Adverse Event occurring during the study period or, if known by the investigator, within 30 days after the patients completion of the study, must as soon as the investigators are informed, be reported by telephone to the appropriate Pfizer Clinical Research Group office regardless of suspected relationship to study drug. (For telephone number please refer to the Ascot Adverse and Serious Adverse Event manual).

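### The SAE exemption covers every endpoint, including any death and renal impairment, with no stated exception for events suspected to be caused by study drug

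*Protocol*

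**What the plan says.** Protocol section IV B 6 a lists all trial endpoints. The secondary list contains "ii) All cause mortality", not restricted to cardiovascular causes. The tertiary list contains "Development of renal impairment" and life-threatening arrhythmias, which include complete heart block. Directly after the lists comes the exemption: "These events are not considered as serious adverse events". On the reporting route, "an event classified as an endpoint must be reported by mail to the Scandinavian Co-ordinating Centre as soon as the investigator is informed". A blinded Endpoint Committee then classifies the event, and confirmed endpoints are passed to the DSMC.

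Section IV B 6 b takes the same line from the other side: "Serious Adverse Events includes any experience which is not a study endpoint that suggests a significant hazard". Its five criteria do not include death, and the hospitalisation criterion is limited to admissions for reasons other than endpoints. An SAE "must as soon as the investigators are informed, be reported by telephone to the appropriate" sponsor office, whatever the suspected relationship to study drug. The investigator must also supply enough detail for an independent judgement of causality.

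The split recurs elsewhere. Section IV B 6 c keeps endpoints off the Adverse Event Form. Section IV B 7 sends discontinuations due to an endpoint to the co-ordinating centre and those due to an SAE to the local sponsor office.

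**The concern.** Exempting adjudicated efficacy events from SAE reporting is a reasonable choice. Here, however, the exemption also covers outcomes that could be harms of the study drugs: death from any cause, renal impairment and complete heart block. The protocol anticipates such harms. Section IV B 6 d sets liver enzyme and creatine kinase rules for the statin/placebo comparison, and section IV B 4 d requires creatinine soon after an ACE inhibitor is started.

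What is at stake is prompt individual notification of the sponsor and a causality work-up for a suspected reaction that happens to be an endpoint. No efficacy estimate or test is affected.

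**Working it through.** No arithmetic applies. The check follows four cases through sections IV B 6 a to c and then tests each provision that might close the gap.

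**Routes**

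| Case | Status under the text | Route |
|---|---|---|
| 1. Suspected reaction, not itself an endpoint, life-threatening or needing admission, patient survives | SAE (criterion 1 or 3) | Telephone to sponsor, with causality information |
| 2. The same reaction, later fatal | SAE when it first qualifies; the death is an endpoint | Telephone first, then mail |
| 3. Suspected reaction where death is the first thing the investigator learns of | Endpoint only | Mail to co-ordinating centre |
| 4. Suspected reaction that is itself an endpoint, such as renal impairment needing admission or complete heart block | Endpoint only; criterion 3 does not apply because the admission is due to an endpoint | Mail to co-ordinating centre |

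Cases 3 and 4 are the gap. Both follow from an express exclusion, not from silence.

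**Provisions that might close it**

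1. *Return from the Endpoint Committee to SAE reporting (IV B 6 a).* This applies only to events judged to be SAEs and not endpoints. Any death meets all-cause mortality, so it cannot be rejected as an endpoint. Confirmed renal impairment or complete heart block likewise stays on the endpoint route.
2. *Catch-all (IV B 6 b).* It sets the preceding criteria aside and asks for immediate reporting of any additional experience that the investigator regards as serious. That could be read to cover a suspected fatal reaction. But it depends on the investigator's view, does not mention endpoints or deaths, and stands beside a flat statement that endpoints are not SAEs. For endpoints it is ambiguous.
3. *Forwarding to the DSMC (IV B 6 a, V B).* Confirmed endpoints arrive after adjudication, at a committee that meets annually or as required. This supports comparison of the arms but gives the sponsor no prompt individual report.
4. *Cause-of-death classification (IV B 5 c).* The categories are coronary, other heart failure, cerebrovascular, other vascular, cancer, and other or unknown. None asks about a drug reaction, so a fatal hepatic or muscle reaction would fall in the last group.

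None of the four clearly requires prompt sponsor notification or a causality assessment in case 3 or 4.

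**The case against.** Several points on the other side stand.

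- Liver failure and rhabdomyolysis are not listed endpoints. Once life-threatening or needing admission they are telephoned, and a later death does not undo that report (case 2). A reader might infer that every fatal reaction is mailed while every non-fatal one is telephoned. The text does not support that: the contrast holds only for case 3, and in case 4 the non-fatal event is mailed too.
- Mail need not mean delay at the site. Both routes start as soon as the investigator is informed, and the paragraph on deaths in IV B 6 a allows for information arriving by telephone. The difference lies in recipient, channel, intervening adjudication and causality work-up.
- A reader might infer that deaths and renal harm are hidden. They are not. All-cause mortality and renal impairment are formal between-arm comparisons in both randomisations (II B, II C). The DSMC receives confirmed endpoints and can call for safety reports more often than yearly. Creatinine is measured on schedule, and under IV B 6 d a laboratory abnormality that changes study drug dosage is recorded as an adverse event.
- The reporting figures and the Adverse and Serious Adverse Event manual are not shown and may contain an exception. That limits certainty, but a manual should not have to override an express exclusion in the protocol.

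It can also be argued that routing all outcomes through blinded adjudication is coherent and avoids site causality opinions in an open-label comparison. That supports keeping the endpoint route. It does not argue against a parallel report when drug causation is suspected.

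**Conclusion.** The point holds in a narrow form. Sections IV B 6 a and b exclude all endpoints from SAE status without an exception for suspected drug causation. The gap consists of deaths that are the first reportable event of a suspected reaction, and suspected drug-caused events that are themselves endpoints.

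Its size cannot be estimated from the documents, which give no rates for mortality, renal impairment or suspected reactions. It is tempting to count all non-cardiovascular deaths as missing. Assuming mortality of 1% to 2% a year and a 40% to 60% non-cardiovascular share, 18,000 × 5 × 0.01 to 0.02 = 900 to 1,800 deaths, and × 0.4 to 0.6 = 360 to 1,080. That figure does not measure the gap. Both rates are assumed, most such deaths need not be suspected reactions, and an admission before death for a non-endpoint cause is already an SAE.

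This is a cheap improvement to the safety wording. The conclusion assumes that the unseen figures and manual add no route.

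**What to change.** Keep the exemption for adjudicated endpoints. Add to IV B 6 a and IV B 6 b that any endpoint, including any death or renal impairment, that the investigator suspects was caused by study drug is also reported at once by the SAE telephone route, in parallel with the endpoint route. Reword the catch-all in IV B 6 b so that it expressly covers endpoints. Check the reporting figures and the manual against the new text. SAE reporting of every non-cardiovascular death is not needed to close this gap.

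The cost is some additional SAE reports through an existing line, and a causality judgement that the protocol does not now ask of investigators, since SAEs are reported regardless of relationship. In the open-label blood pressure comparison that judgement is made knowing the treatment. It should stay out of the material sent to the Endpoint Committee, so that blinded adjudication and every planned analysis are unchanged.

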randomised. In the UK those doctors who wish to treat their patient with lipid lowering therapy (statin or fibrate) should inform the relevant study centre before randomisation. Any subjects who wish to drop out for any reason during this early run-in period will be encouraged not to continue in the study. Subjects will be randomised only if, at the end of the run-in, they seem likely to comply with the trial protocol for several more years. By this process it is anticipated that many potential drop-outs will be excluded before becoming part of the randomised comparison, with a consequent improvement in statistical sensitivity.

- Subjects whose triglyceride level was $>4.5\text{mmol/l}$ or glucose was $>7.0\text{mmol/l}$ at screening will be recalled during this period for a fasting blood sample to evaluate eligibility (see sections IV A1 and IV A3).

c. Randomisation visit (0 months)

- Physical examination.
- BP and HR.
- Fasting blood sample: total cholesterol, HDL, triglycerides, and glucose.
- 12 lead ECG (to be posted to ASCOT Scandinavian Co-ordinating Centre, Gothenburg University Clinical Research Institute, [name], Sweden).
- Eligibility and consent confirmed.
- Randomisation allocated using minimisation procedures by the appropriate co-ordinating centre by telephone.
- All previous antihypertensive medication withdrawn. Continue and record all other existing medication.
- Study medication allocated (see section IV B3).
- Appointment made for next visit.
- Adverse events (including hospitalisation, diagnosis, duration) recorded.

d. First follow-up visit (6 ± 2 weeks)

- Endpoints recorded.
- Adverse events (including hospitalization, diagnosis, duration) recorded.
- BP and HR.
- Non-fasting blood sample for electrolytes and creatinine, if started on an ACE inhibitor at 0 months. (This test is required within a few weeks of initiating an ACE inhibitor at any point in the trial).
- BP treatment modified if BP above target (see section IV B3).
- Changes in medication recorded.
- Study medication allocated.
- Appointment made for next visit.

e. Second follow-up visit (3±1 months)

- Endpoints recorded.
- Adverse events recorded.
- BP and HR.
- BP treatment modified if BP above target (see section IV B3).
- Changes in medication recorded.
- Study medication allocated.
- Appointment made for next visit.

f. Third follow-up visit (6±1 month)

- Endpoints recorded.
- Adverse events recorded.
- BP and HR.

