- Fasting blood sample: total cholesterol, HDL, triglycerides, glucose, electrolytes, creatinine and, if randomised to statin/placebo, liver function tests (LFT's).
- Urine: stix for protein, blood and sugar.
- BP treatment modified if BP above target (see section IV B3).
- Changes in medication recorded.
- Study medication allocated.
- Appointment made for next visit.

g. Subsequent follow-up visit (year 1, 2, 3, 4, 5 ± 1 month)

- Body weight.
- Endpoints and adverse events recorded.
- BP and HR.
- ECG at year 2 only.
- Fasting blood sample: Hb, total cholesterol, HDL, triglycerides, glucose, electrolytes, creatinine, liver function tests (LFT's), and at year 2 only extra blood for frozen storage.
- Urine: stix for protein, blood and sugar.
- BP treatment modified if BP above target (see section IV B3).
- Changes in medication recorded.
- Study medication allocated.
- Appointment made for next visit.

h. Follow-up visit (years 1½, 2½, 3½, 4½, 5½ ± 1 month)

- Endpoints and adverse events recorded.
- BP and HR.
- Smoking and alcohol intake recorded.
- BP treatment modified if BP above target (see section IV B3).
- Study medication allocated.
- Appointment made for next visit.

i. Extra visits

In addition it may be necessary to arrange extra visits to control or monitor blood pressure or for other reasons. The timing of all visits and any extra visits should be recorded in the case record forms, including the reason for the visit and any extra laboratory tests or procedures carried out.

j. Final visit

All participating subjects should have a final assessment at the end of the study. This assessment should include:

- Endpoints and adverse events recorded.
- BP and HR.
- Body weight measurements.
- Smoking and alcohol intake recorded.
- ECG.
- Fasting blood sample for lipid profile; HB, glucose, creatinine, electrolytes and liver function tests (LFT's), and extra blood for frozen storage.
- Urinalysis with stix for microalbuminuria, protein, blood and sugar.
- Changes in medication recorded.

As one arm of the trial has been discontinued before the other, a final visit examination will be performed for the patients involved in the discontinued arm of the trial. These patients will then continue in the remaining arm of the trial until the study is finally terminated, when a final visit for that limb of the trial will also be carried out.

k. SUMMARY SCHEDULE OF EVENTS

1 2 3 4 5 6 7 8 9

MONTHS	-1	0	1.5	3	6	12	18	24	30	36	42	48	54	60†	66/ final

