For all Serious Adverse Events, the investigator is obliged to pursue and provide information as requested by the clinical monitor in addition to that on the case record form. In general, this will include a description of the event in sufficient detail to allow for a complete medical assessment of the case and independent determination of the causality. The investigator should ensure that information on such cases reported by telephone or other means and information entered in the case record forms are accurate and consistent.

Serious Adverse Events will be handled as follows:

Serious Adverse Event Reporting Pathway

The DSMC is responsible for advising the steering committee concerning the protocol amendments or study discontinuation based on this information. The yearly safety report will not contain any information on the treatment arm, if the DSMC has not detected any safety issues. If deemed necessary by the DSMC, safety reports will be issued more frequently than the stipulated 1 year interval.

c. Non Serious Adverse Events

All ongoing Adverse Events at each visit, regardless of treatment, if not a study endpoint will be recorded on the Adverse Event Form. A follow-up of the events is required at each of the following visits until such time that the event is resolved. (For further details please refer to the ASCOT Adverse and Serious Adverse Event manual).

d. Abnormal Laboratory Test Results

The recorded results of all laboratory tests required by the protocol will be attached to the case record form. All clinically important abnormal laboratory tests occurring during the study will be repeated at appropriate intervals until they return either to baseline or to a level deemed acceptable by the investigator and the clinical monitor, or until a diagnosis that explains them is made. Abnormal laboratory test results that result in a change in study drug dosage should be recorded as adverse events in the case record form.

For patients randomised to atorvastatin or placebo:

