Alanine transaminase (ALT) x 4 upper limit of normal (ULN) is to be checked after approximately 1 week, while $ALT > 2xULN$ but $\leq 4xULN$ is to be checked after approximately 3 weeks. If repeat $ALT > 4xULN$ then statin/placebo treatment should be stopped temporarily; whereas if > 2 but $\leq 4xULN$, ALT is to be checked again after approximately 3 weeks, with study treatment then stopped temporarily if ALT remains $> 2xULN$. After stopping study treatment temporarily, ALT is to be checked again after approximately 6 weeks and study treatment stopped permanently if still more than $1.5xULN$ (with 3 week follow up visits) until ALT reverts to normal: ie $\leq 1.5xULN$). If, on the other hand, $ALT \leq 1.5xULN$, then the allocated study treatment can be started again, with a further 2 early recall visits at 3-week intervals (at which ALT must remain $\leq 2xULN$, otherwise study treatment is to be stopped permanently).

Creatine kinase (CK): symptoms of myopathy (ie new unexplained muscle pain or weakness) accompanied by an otherwise unexplained elevation of $CK > 10xULN$ should result in the study treatment being stopped permanently (with 3-week follow up visits until CK reverts to normal: ie $\leq 3xULN$). $CK > 4xULN$ but $\leq 10xULN$ that cannot be explained (ie by some trauma, intramuscular injection, heavy exercise, recent myocardial infarction etc) is to be checked after approximately 1 week and, if repeat $CK > 4xULN$ then study treatment should be stopped temporarily. CK is to be checked again after approximately 6 weeks and study treatment stopped permanently if still $> 3xULN$. If, on the other hand, $CK \leq 3xULN$, then the allocated

study treatment can be started again, with a further 2 early recall visits at 3-week intervals (at which CK must remain $\leq 3 \times \text{ULN}$, otherwise study treatment is to be stopped permanently). A flow chart detailing the investigations to be undertaken is located in the Ascot laboratory manual.

e. Breaking the Randomisation Code: Emergency Procedures

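### Section IV B 6 c requires only adverse events still ongoing at a visit to be recorded, while the visit lists in IV B 4 set no such limit; followed literally, 6 c would miss most short non-serious events

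*Protocol*

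**What the plan says.** Protocol section IV B 6 c (Non Serious Adverse Events) gives the rule for the form: "All ongoing Adverse Events at each visit, regardless of treatment, if not a study endpoint will be recorded on the Adverse Event Form". It continues: "A follow-up of the events is required at each of the following visits until such time that the event is resolved". It then points to a manual that is not at hand: "For further details please refer to the ASCOT Adverse and Serious Adverse Event manual".

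The visit lists in IV B 4 are worded differently:

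- Randomisation (4 c): "Adverse events (including hospitalisation, diagnosis, duration) recorded".
- 6 weeks (4 d): "Adverse events (including hospitalization, diagnosis, duration) recorded".
- 3 and 6 months (4 e, 4 f): "Adverse events recorded".
- Yearly, half-yearly and final visits (4 g, 4 h, 4 j): endpoints and adverse events are to be recorded, with no further qualification.

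None of these lists uses the word ongoing. Scheduled visits fall at 6 weeks, 3 months and 6 months, and every 6 months after that. Section IV B 4 i also allows unscheduled visits: "In addition it may be necessary to arrange extra visits to control or monitor blood pressure or for other reasons".

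**The concern.** Section 6 c is the only text in the Protocol that defines what goes on the Adverse Event Form. Its logic is to find an event that is open at the visit and follow it until it closes. It gives no instruction for an event that opened and closed since the last visit. The visit lists can be read as asking for such events, and the request for duration at two visits fits completed events better than open ones. From month 3 onward, however, no list asks for duration or sets a look-back period. A site could follow either text and consider itself compliant, so recording may differ between sites.

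Two consequences would follow under 6 c. The incidence of short non-serious events would be understated. The recorded rate would also depend on how often a patient is seen. The second matters because extra visits in the open-label blood pressure comparison are driven partly by blood pressure control, and in the lipid limb IV B 6 d adds recall visits triggered by laboratory results. Neither kind of visit need be equally frequent in the groups compared.

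**Working it through.** The Protocol gives no figure for adverse event capture, so there is nothing to reproduce. The check works out what the literal wording of 6 c implies.

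**Inputs from the Protocol.** Scheduled visits at 0, 1.5, 3, 6, 12, 18, …, 60 months (IV B 4), which is 12 visits after randomisation over 5 years. From month 6 the interval is L = 6 × 365.25/12 = 182.6 days.

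**Assumptions.** Event durations are not given, so a range is used. Onset is uniform over the interval between visits.

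**Formula.** An event of fixed duration d is ongoing at the next visit with probability min(1, d/L). Over the whole schedule, capture is the sum of min(d, interval length) across intervals, divided by 5 years (1826.25 days).

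**One 6-month interval.**

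- 14 days: 14/182.6 = 7.7%
- 30 days: 30/182.6 = 16.4%
- 91 days: 91/182.6 = 49.8%

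**Whole 5-year schedule, and sensitivity to visit frequency.** The last column assumes one extra visit midway in each of the nine 6-month intervals, giving 12 + 9 = 21 visits.

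| Duration | One 6-month interval | 5-year schedule | With assumed extra visits |
|---|---|---|---|
| 7 days | 3.8% | 4.6% | 8.0% |
| 14 days | 7.7% | 9.2% | 16.1% |
| 30 days | 16.4% | 19.7% | 34.5% |
| 60 days | 32.9% | 37.9% | 67.4% |
| 91 days | 49.8% | 54.8% | 99.7% |

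For example, at 14 days the schedule gives 12 × 14/1826.25 = 9.2%, and the added visits give 21 × 14/1826.25 = 16.1%. For short events the ratio is simply the ratio of visit counts, 21/12 = 1.75.

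**Check on the fixed-duration assumption.** With exponential durations of mean d, capture in one interval is (d/L)(1 − exp(−L/d)). This gives 7.7% at 14 days, 16.4% at 30 days and 43.1% at 91 days, so the results for short events do not change.

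**Under the alternative reading.** If every event since the last visit is recorded, capture does not depend on duration or visit count, apart from recall.

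**The case against.** The strongest reply is that the visit lists already ask for adverse events without the restriction, and that the manual cited in 6 c may say how resolved events are handled. The schedule of events points the same way: its row for current illness and adverse events is marked at every visit, with a note that only current illness is recorded at the screening visit, which suggests that later visits collect more. This stands to the extent that a reader may not conclude that short events are never captured. It does not remove the contradiction, because the one section that defines the form is the restrictive one.

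A reader might also infer that resolved muscle symptoms in the statin comparison leave no trace. The Protocol does not support that. IV B 6 d mentions "symptoms of myopathy (ie new unexplained muscle pain or weakness") only together with a CK rise above 10 times the upper limit of normal, as a trigger for permanently stopping study treatment. Such a case is documented through the discontinuation record in IV B 7. Milder symptoms that have settled depend on which wording a site follows, like any other short event.

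A third tempting inference is that one blood pressure regimen's adverse event rate is inflated. Two extra visits in year 1 in one arm only would give 6/4 = 1.5 for short events in that year. Over the 5-year schedule the same two visits give 14/12 = 1.17. Both figures rest on an assumed imbalance. The Protocol gives no visit counts by arm, and both regimens have six titration steps to the same targets.

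The objectives (II A to II C) and the analysis section (V E 2) name no comparison of adverse event rates, so it cannot be said that a planned tolerability analysis rests on this form. Recording only what is present at a visit could also be defended as a deliberate simplification in a trial of 18,000. If that was the intention, the visit lists should say so.

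**Conclusion.** The Protocol contradicts itself on which non-serious adverse events are recorded, and the more restrictive text would lose most short events. Read literally, and with uniform onset, 6 c would catch about 8% of 2-week, 16% of 1-month and 50% of 3-month events in a 6-month interval. Over the full 5-year schedule, with its closer early visits, the figures are about 9%, 20% and 55%. Capture would also vary with visit frequency.

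The finding is limited in three ways. Actual losses depend on which text sites follow and on what the manual says. Serious events are reported as soon as the investigator learns of them; laboratory abnormalities that change dosage and reasons for stopping study drug are also recorded separately. Unequal visit frequency could bias a comparison between arms, but its direction and size cannot be established from the document.

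The issue concerns the completeness of non-serious safety data. The primary endpoint, sample size and alpha are not affected. It is worth correcting because a stated rule, read as written, understates incidence.

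**What to change.** Reconcile the two sections by replacing the opening phrase of 6 c, which limits recording to ongoing events, with: *All adverse events that started, worsened or were ongoing since the previous visit, including those already resolved, with start and stop dates*. Keep the sentence on follow-up until resolution. State that the rule applies equally at scheduled and extra visits, and align the adverse event manual.

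The cost is one sentence in the Protocol, a check of the manual, and more entries per visit. Some entries would rest on patient recall over up to 6 months, which in the open-label blood pressure limb may be influenced by knowledge of treatment. Start and stop dates would at least allow events that had resolved before the visit to be separated from those present at it, so that both can be tabulated.
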